## 8 Visit schedule and assessments

[Table 8-1](#) lists all of the assessments and indicates with an “X”, the visits when they are performed. All data obtained from these assessments must be supported in the subject’s source documentation.

Subjects should be seen for all visits/assessments as outlined in the assessment schedule ([Table 8-1](#)) or as close to the designated day/time as possible. Missed or rescheduled visits should not lead to automatic discontinuation. Subjects who prematurely discontinue the study for any reason should be scheduled for a visit as soon as possible, at which time all of the assessments listed for the final visit will be performed. At this final visit, all dispensed investigational product should be reconciled, and the AE and concomitant medications recorded on the CRF.

If the subject cannot or is unwilling to attend any visit(s), the site staff should maintain regular telephone contact with the subject, or with a person pre-designated by the subject. This telephone contact should preferably be done according to the study visit schedule.

The table indicates which assessments produce data to be entered into the clinical database (D) or remain in source documents only (S) (“Category” column).

Allowed visit windows are specified as follows:

- Screening assessments must occur within 84 days (12 weeks)  $\pm$  7 days prior to the enrollment as per [Table 8-1](#).
- For all screening visits a general  $\pm$  7 day visit window is allowed
- A  $\pm$  7 day visit window is allowed at Week 1 Day 1 (calculated from day of consent)
- A  $\pm$  3 day visit window is permitted on assessments at Week 3 Day 1.
- For all other dosing visits a general  $\pm$  7 day visit window is permitted on assessments
- A  $\pm$  7 day visit window for the end of treatment phase (last infusion + 2 weeks) is allowed.
- A + 7 day visit window for the end of the safety follow-up phase (last infusion + 105 days) is allowed.

Every effort should be made to follow the schedule outlined in [Table 8-1](#).

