##### **Supportive analyses**

- The supportive analyses described below will be performed on all FAS subjects who have completed 26 weeks on treatment. Missing values will be imputed as stated in [Section 12.4.3](#).Annualized priapic Events Rate: The annualized rate of priapic events is defined as the total number of priapic events for a subject occurring from the date of initial infusion to the last contact date of the Treatment Phase of the study  $\times$  365.25 divided by the number of days during that same time period. This calculation accounts for early dropouts or lost to follow-up by extrapolating the priapism events rate of every subject to 1 year.

- Percent reduction from baseline in priapic events will also be assessed by Week 52.
- The total number of priapic episodes in the screening period (12 weeks baseline) will be compared to the total number of priapic episodes occurring in the first 12 weeks on treatment (0-12 weeks) using a nonparametric test (i.e. Wilcoxon's Sign Rank test). Additionally, a similar analysis will be performed to compare to the total number of priapic episodes occurring in the last 12 weeks on treatment (15-26 weeks).
- Number of priapic events will be summarized in the screening period (12 weeks baseline), in first 12 weeks on treatment (0-12 weeks), and in the last 12 weeks on treatment (15-26 weeks) and percent reduction from baseline will also be summarized.

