2.5.6 Supportive analyses

The supportive analyses described below will be performed on all FAS patients who have completed 26 weeks on treatment. Missing values will be imputed as stated in [Section 2.5.4](#)

Supportive analysis 1:

Annualized priapic Events Rate: The annualized rate of priapic events is defined as the total number of priapic events for a subject occurring from the date of initial infusion to the last contact date of the Treatment Phase of the study \times 365.25 divided by the number of days during that same time period. This calculation accounts for early dropouts or lost to follow-up by extrapolating the priapism events rate of every subject to 1 year.

Supportive analysis 2:

Percent reduction from baseline in priapic events will also be assessed by Week 52. Assuming uniformity in the occurrence of priapic events before exposure to crizanlizumab treatment, baseline will be adjusted for 52 weeks for analysis purpose.

Baseline (adjusted for 52 weeks): Number of priapic events in 12 weeks screening period \times (52/12) and percentage change from baseline = (Post baseline value – Baseline (adjusted to 52 weeks) value) \times 100 / Baseline (adjusted to 52 weeks) value.

Percentage reduction from baseline is the negative percentage change from baseline.

Supportive analysis 3:

The total number of priapic episodes in the screening period (12 weeks baseline) will be compared to the total number of priapic episodes occurring in the first 12 weeks on treatment (0-12 weeks) using a nonparametric test (i.e. Wilcoxon's Sign Rank test). Additionally, a similar analysis will be performed to compare to the total number of priapic episodes occurring in the last 12 weeks on treatment (15-26 weeks). For the analysis purpose, for 0-12 weeks: Day 1 to Day 84 and for 15-26 weeks: Day 105 to Day 182 will be used.

Supportive analysis 4:

Number of priapic events will be summarized in the screening period (12 weeks baseline), in first 12 weeks on treatment (0-12 weeks), and in the last 12 weeks on treatment (15-26 weeks) and percent reduction from baseline will also be summarized. For the analysis purpose, for 0-12 weeks: Day 1 to Day 84 and for 15-26 weeks: Day 105 to Day 182 will be used.

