2.6.2 Statistical hypothesis, model, and method of analysis

Similar analyses on percent reduction in acute priapic events for subjects from full analysis set will be conducted, as done for primary endpoint.

Annualized rates will be calculated for the secondary endpoints.

The annualized rate of events is defined as the total number of events for a subject occurring from the date of initial infusion to the last contact date of the Treatment Phase of the study x 365.25 divided by the number of days during that same time period. This calculation accounts for early dropouts or lost to follow-up by extrapolating the priapism events rate of every subject to 1 year.

Annualized events rate = Total number of events x 365.25 / (end date – treatment start date +1), where end date is defined as the minimum of (last dose date until treatment discontinuation + 27 days, date of initiation or discontinuation of HU/HC or L-glutamine - or other therapies to treat SCD and or to prevent/reduce VOCs such as voxelotor and erythropoietin, cut-off date).

Descriptive summary statistics including n, mean, standard deviation (SD), lower quartile (Q1), median, upper quartile (Q3), minimum, and maximum will be presented for the annualized rate of events and number of priapic events at Baseline, by Week 26 and by Week 52 .

The change from baseline in rates of events at Week 26 (i.e. evaluation at Week 27, Day 1) and Week 52 (i.e. evaluation at Week 53, Day 1) will be summarized by n, mean, median, standard deviation (SD), lower quartile (Q1), median, upper quartile (Q3), and minimum and maximum.

Graphical representation of annualized rates, through box plots or bar graphs or swimmer plot, as appropriate, will also be performed.

The Annualized Rates of Events at Week 26 (i.e. evaluation at Week 27, Day 1) and Week 52 (i.e. evaluation at Week 53, Day 1) will be summarized by n, mean, standard deviation (SD), lower quartile (Q1), median, upper quartile (Q3), standard deviation and minimum and maximum.

Additionally, cumulative number of acute priapic events, uncomplicated and complicated VOC events will also be summarized over time (like 0-12 weeks, 0-26 weeks, 0-40 weeks and 0-52 weeks).

Subgroup analyses displaying annualized rate, for complicated and uncomplicated VOC events will be performed based on use of hydroxyurea versus no use of hydroxyurea by 26 weeks and 52 weeks.

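### SAP 2.6.2 gives two end dates for the annualised event rate and does not say that events after the formula's end date are excluded

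*SAP*

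**What the plan says.** SAP 2.6.2 describes the annualised rate for the secondary endpoints twice, in consecutive paragraphs.

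- **Prose.** Events are counted "from the date of initial infusion to the last contact date of the Treatment Phase of the study", scaled to a year and "divided by the number of days during that same time period". Numerator and denominator therefore cover one period, ending at the last treatment-phase contact.
- **Formula.** It begins "Annualized events rate = Total number of events x 365.25" and divides by the days from treatment start to an end date, "where end date is defined as the minimum of (last dose date until treatment discontinuation + 27 days". The other two terms of the minimum are the "date of initiation or discontinuation of HU/HC or L-glutamine - or other therapies to treat SCD", and the cut-off date. No window is attached to the event count.

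Other sections bear on the same rate:

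- SAP 2.5.6, Supportive analysis 1, has only the prose version, ending at the "last contact date of the Treatment Phase of the study". Protocol 12.4.4 does the same and adds: "This calculation accounts for early dropouts or lost to follow-up by extrapolating the priapism events rate of every subject to 1 year".
- SAP 2.1.1 sets counting windows for tables and figures. By-Week-26 results run from first dose to the day before the Week 27 Day 1 visit, and by-Week-52 results to the day before the Week 53 Day 1 visit.
- SAP 2.6.3, on intercurrent events for the secondary endpoints, is marked not applicable.
- SAP 2.6.1 restricts the secondary efficacy analyses to subjects in the full analysis set who completed 26 and 52 weeks on treatment.

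**The concern.** A rate is interpretable only if events and follow-up time come from the same interval. Section 2.6.2 gives two intervals and never says that the shorter one also limits the event count. The primary analysis has that sentence: SAP 2.5.3 states that only data before the therapy change are used. Section 2.6.2 has no equivalent.

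The affected subject is foreseen. Protocol 6.2.1.1 says that a medically necessary change to hydroxyurea, L-glutamine or voxelotor should not by default end trial participation, so such subjects stay and keep reporting events.

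The formula also has no Week 26 or Week 53 term, although rates are reported by both time points. Whether it respects the SAP 2.1.1 windows depends on what cut-off date means. SAP 2.1 uses the term for the data cut-off and says the final analysis has none; SAP 2.1.1 uses it for the visit limit.

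At stake are the rates of priapic events, uncomplicated vaso-occlusive crises and complicated crises, and their changes from baseline, in a trial with no control arm.

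**Working it through.** The plan states no numerical annualised rate, so there is no figure to reproduce. The check compares the number of days over which events are counted with the number of days in the denominator.

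**Inputs**

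- Illustrative constant rate: 10 events per 26 weeks (182 days), the planning mean in SAP Section 3. The ratios below do not depend on this value.
- Last infusion at Week 51 (Protocol Table 6-1), which is Day 351 (SAP 2.1.1, visit-window table).
- End-of-treatment visit: Protocol Section 8 places it at last infusion + 2 weeks ("visit window for the end of treatment phase (last infusion + 2 weeks) is allowed"; the allowance is 7 days either side). 351 + 14 = Day 365, which is Week 53 Day 1.
- SAP 2.1.1 windows with visits on schedule: events counted to Day 182 (by Week 26) and Day 364 (by Week 52).
- Denominator: end date − start date + 1, which equals the study-day number of the end date.

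**Matched windows.** True annualised rate = 10 × 365.25 / 182 = 20.07. If events are also cut at a Day 91 therapy change, 5 events × 365.25 / 91 = 20.07. There is then no distortion.

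**Therapy change, events not cut at the formula's end date.** Ratio to the true rate = days counted / day of change.

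| Change on | By Week 26 | By Week 52 |
|---|---|---|
| Day 91 | 182/91 = 2.0 (rate 40.1) | 364/91 = 4.0 (rate 80.3) |
| Day 182 | 182/182 = 1.0 | 364/182 = 2.0 (rate 40.1) |
| Day 273 | not affected | 364/273 = 1.33 (rate 26.8) |

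If all 34 evaluable subjects had the same true rate, one Day 91 change would raise the cohort mean by (2.0 − 1)/34 = 2.9% by Week 26 and (4.0 − 1)/34 = 8.8% by Week 52. One subject in 34 would hardly move the median. The documents do not say how many subjects change therapy.

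**52-week completer, no therapy change.** The last-dose term gives 351 + 27 = Day 378.

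- Events counted to Day 364 (SAP 2.1.1): 364/378 = 0.963, or −3.7%.
- Events counted to the last contact at Day 365 (prose): 365/378 = 0.966, or −3.4%.
- Final visit 7 days late or early, SAP 2.1.1 window: 371/378 = 0.981 (−1.9%) or 357/378 = 0.944 (−5.6%).

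This shortfall disappears if cut-off date in the formula means the Week 53 Day 1 limit.

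**The case against.** The strongest reply is that the prose requires the same period above and below the line, so the formula's end date simply closes that one period for both. The SAP's document history, which describes the addition as an end-date definition for the rate, fits this reading. Programming specifications are held in separate documents and may settle it. If events are cut at the end date, the therapy-change inflation vanishes. A reader might infer that the plan prescribes a mismatched rate; the same-period wording does not support that. What stands is that the two end dates differ and no sentence applies the second to the event count.

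Event collection may also continue past the end-of-treatment visit: Protocol 8.2.1 asks for priapic events throughout the study period, and Table 8-2 covers crises during follow-up. Events to Day 378 might therefore be available, except where the 105-day follow-up is waived. Counting them would contradict the SAP 2.1.1 window, so the inconsistency remains.

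Two further readings go too far.

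- Last dose + 27 days does not shorten a completer's denominator. It falls after the Day 365 visit.
- Large understatement for subjects who stop early does not follow. SAP 2.6.1 limits these analyses to completers, and the general remark about early dropouts does not override that.

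Supportive analysis 1 is separately labelled, so a different value there is not in itself an error. It should say how it differs.

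**Conclusion.** The point holds as an inconsistency that should be corrected before programming. SAP 2.6.2 gives two end dates for one rate, does not limit the event count to the formula's end date, and does not tie the formula to the SAP 2.1.1 windows.

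For a subject whose therapy changes on Day 91, the literal reading gives 2.0 times the true rate by Week 26 and 4.0 times by Week 52. This assumes a constant event rate, continued reporting, and events not cut at the change. For a 52-week completer the understatement is about 3.5%, assuming on-schedule visits and that cut-off date is not the visit limit.

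The two errors run in opposite directions: the first raises on-treatment rates, against the drug, and the second lowers them slightly. A reader might infer that the trial's efficacy conclusion is at risk. The documents do not support that: the rates are summarised descriptively with medians and quartiles beside the means, no test is specified for them, and the primary test and sample size do not use this formula.

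**What to change.** In SAP 2.6.2, define one end date for both numerator and denominator, as the earliest of:

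- last dose + 27 days;
- the first SCD therapy change after first dose;
- the last date on which event reports were collected;
- the SAP 2.1.1 limit for the rate being reported (the day before Week 27 Day 1 or Week 53 Day 1);
- the data cut-off, named as such.

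State that only events with onset on or before that date are counted. Apply the same definition in Supportive analysis 1 (SAP 2.5.6), or label that analysis as not censored at therapy change. Record the difference from Protocol 12.4.4 in SAP Section 4, which does not now list it.

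The cost is a few lines of SAP text and one filter on event onset date. No new data are needed.

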All statistical analyses will be performed using all data collected in the database up to the data cut-off date. All data with an assessment date or event start date (e.g., vital sign assessment date or start date of an adverse event) prior to or on the cut-off date will be included in the analysis. Any data collected beyond the cut-off date will not be included in the analysis and will not be used for any derivations at the time of the primary analysis.

All events with start date before or on the cut-off date and end date after the cut-off date will be reported as 'ongoing'. The same rule will be applied to events starting before or on the cutoff date and not having documented end date. This approach applies, in particular, to adverse event and concomitant medication reports. For these events, the end date will not be imputed and therefore will not appear in the listings.

For the final analysis, all data collected will be used, without notion of cut-off date.

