2.1.1 General definitions

Study treatment: Study treatment refers to Crizanlizumab (SEG101) 5.0 mg/kg provided by IV infusion.

Study treatment start and end date: Study treatment start date is defined as the first date when a non-zero dose of study drug is administered and recorded on the Drug Administration Record (DAR) CRF page. Similarly, study drug end date is defined as the last date when a non-zero dose of study drug is administered and recorded on the DAR CRF page of the core study.

Baseline: Baseline period is defined as 12 weeks screening period prior to the first infusion of crizanlizumab 5 mg/kg at Week 1 Day 1.

- For the analysis purpose, in the tables and figures, baseline is considered from Day -91 to one day prior to dosing. Similarly, for "by week 26 analysis" from the first dose date to one day prior to Week 27 Day 1 visit date and for "by week 52 analysis" from the first dose date to one day prior to Week 53 Day 1 visit date will be considered.
- For subjects missing "Week 27 Day 1" visit or "Week 53 Day 1" visit, the scheduled visit day will be considered for cut-off.
- For listings, all available data will be considered.

For safety evaluations, the last available assessment on or before the date of start of study treatment is taken as "baseline" assessment. In case time of assessment and time of treatment start is captured, the last available assessment before the treatment start date/time is used for baseline.

For safety parameters (e.g. ECGs), where study requires multiple replicates per time point, the average of these measurements will be calculated for baseline (if not already available in the database).

In cases where multiple measurements meet the baseline definition, with no further flag or label that can identify the chronological order, then the following rule should be applied: If values are from central and local laboratories, the value from central assessment should be considered as baseline. If multiple values are from the same laboratory (local or central) or collected for ECGs or vital signs, then the last entry should be considered as baseline.

If subjects have no value as defined above, the baseline result will be missing.

Post baseline: Any measurements taken after baseline will be considered as post-baseline measurements.

Change from baseline: Post baseline value – baseline value

Percent change from baseline: (Post baseline value – baseline value) *100/ Baseline value;
(relative change from baseline).

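### SAP 2.6.2 defines the annualised event rate in two ways that do not agree, and the formula does not limit the events counted to the period it divides by

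*SAP*

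**What the plan says.** SAP 2.6.2 annualises the secondary event rates and defines the calculation twice, in consecutive paragraphs.

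- **Prose.** The numerator is the "total number of events for a subject occurring from the date of initial infusion to the last contact date of the Treatment Phase", and the total is "divided by the number of days during that same time period". Events and days share one window.
- **Formula.** It begins "Annualized events rate = Total number of events x 365.25" and divides by the days from treatment start to an end date, "where end date is defined as the minimum of (last dose date until treatment discontinuation + 27 days". The other terms in the minimum are the "date of initiation or discontinuation of HU/HC or L-glutamine", the same for other SCD or VOC therapies, and the cut-off date. Nothing limits the event total to events on or before the end date.

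Four other places bear on this:

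- SAP 2.1.1 sets the by-Week-52 window as "from the first dose date to one day prior to Week 53 Day 1 visit date will be considered", with a parallel rule for Week 26. Neither window stops at a therapy change.
- SAP 2.1 says: "For the final analysis, all data collected will be used, without notion of cut-off date".
- SAP 2.5.6 (supportive analysis 1) and Protocol 12.4.4 give only the prose definition. The SAP document history mentions that an end date was added, but SAP Section 4 does not list it as a change from the protocol.
- Intercurrent event 4b (SAP 1.2.1 and 2.5.3) covers starting or stopping SCD therapies and also prophylaxis for priapism. The end-date list in 2.6.2 has the SCD therapies but not the prophylaxis. SAP 2.6.3 declares intercurrent-event handling not applicable to the secondary endpoints.

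**The concern.** A programmer has to choose an event count to put over the formula's days. The only total defined in 2.6.2 runs to the last treatment-phase contact, and the general windows in 2.1.1 also run past a therapy change. Coding the formula as it stands can therefore put a full-period count over a shortened period.

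The situation can arise. Protocol 6.2.1.1 says that a medically necessary change of HU/HC, L-glutamine or voxelotor should not by default end participation, so such subjects can complete treatment and enter the secondary analyses, which SAP 2.6.1 restricts to completers. SAP 2.6.2 also plans annualised VOC rates by hydroxyurea use, where subjects who change hydroxyurea matter directly.

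At stake are the reported secondary rates of priapic events and of uncomplicated and complicated VOCs. Supportive analysis 1 could also report an annualised priapic rate that differs from the secondary one without explanation.

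**Working it through.** The plan states no figure for the annualised rate, so there is none to reproduce. The check compares the possible readings.

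**Inputs**

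- Last scheduled dose: Week 51 Day 1 = Day 351 (Protocol 6.1; SAP 2.1.1, visit-window table).
- Week 53 Day 1 = Day 365, so the Week 52 window ends on Day 364 on schedule (SAP 2.1.1). The Week 26 window ends on Day 182.
- Illustrative event rate: the planning baseline of 10.0 (SAP Section 3), taken as per 26 weeks, less 25% = 7.5 per 26 weeks, or 15 by Day 364.
- Assumptions, because the documents give no figures: a constant event rate within subject; a change of SCD therapy on Day 92, 183 or 274; 1 to 5 of 34 subjects changing.

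**Step 1: consistent readings.** Rate = events × 365.25 / days.

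- Prose window for both: 15 × 365.25 / 364 = 15.05 per year.
- Formula end date for both, change on Day 92: (7.5 × 92/182) × 365.25 / 92 = 15.05 per year.

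At a constant rate the two agree, so neither inflates anything.

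**Step 2: prose count over formula days.** The inflation factor is L/c, where L is the last day counted and c is the day of change.

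| Window | Day of change c | Rate per year | Factor L/c |
|---|---|---|---|
| Week 52 (L = 364) | 92 | 15 × 365.25/92 = 59.6 | 3.96 |
| Week 52 | 183 | 15 × 365.25/183 = 29.9 | 1.99 |
| Week 52 | 274 | 15 × 365.25/274 = 20.0 | 1.33 |
| Week 26 (L = 182) | 92 | 7.5 × 365.25/92 = 29.8 | 1.98 |
| Week 26 | 137 | 7.5 × 365.25/137 = 20.0 | 1.33 |

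A change on Day 91 gives exactly 364/91 = 4.0 by Week 52.

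**Step 3: effect on the group mean by Week 52.** With k of 34 subjects changing and the same underlying rate in all, the relative shift is (k/34) × (364/c − 1).

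| k | c = 92 | c = 183 | c = 274 |
|---|---|---|---|
| 1 | +8.7% | +2.9% | +1.0% |
| 3 | +26.1% | +8.7% | +2.9% |
| 5 | +43.5% | +14.5% | +4.8% |

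The median would move much less.

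**Step 4: completers with no therapy change.** If no cut-off applies, the formula's end date is Day 351 + 27 = Day 378. With events counted to Day 364, the rate is too low by 1 − 364/378 = 3.7%. With events counted to a last contact on Day 365, it is too low by 1 − 365/378 = 3.4%.

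**Step 5: priapism prophylaxis.** Protocol 6.2.1.2 foresees that prophylaxis may be altered or stopped during the study. Under 4b the primary analysis discards data after it is started or stopped; the end-date list in 2.6.2 does not. This creates no arithmetic mismatch. It leaves time after such a change in the priapic event rate, the endpoint it is most likely to affect.

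**The case against.** The strongest reply is that the prose requires events and days to cover the same period, and the formula follows directly as its operational version. On that reading the count stops at the formula's end date too, and nothing is inflated. This shows what was intended, and it stands. A reader might infer from the fourfold figure that the plan's rates are wrong, or that every subject who changes therapy is overstated. The documents do not support that: the inflation needs the prose count to be combined with the formula's days, and the factors are constructed illustrations. Therapy changes are also restricted (Protocol 5.1, criterion 6, and 6.2.1.1), and medians and quartiles are among the planned summaries.

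A second reply is that the cut-off in the minimum may mean the Week 27 or Week 53 visit, since SAP 2.1.1 uses that term when such a visit is missing. The understatement in completers would then largely disappear. That reading is fair, so the 3.4% to 3.7% is conditional. A reader who takes the missing cap literally might also put a Week 26 count over 378 days (182/378 = 0.48). The windows in 2.1.1 make that an unlikely intention, and it is not claimed here as an effect.

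A third reply is that 4b belongs to the primary estimand, and SAP 1.2.2 and 2.6.3 declare secondary estimands and intercurrent-event handling not applicable. Nothing therefore obliges the secondary rates to follow 4b, and leaving out a priapism-only therapy is defensible for the VOC rates. That also stands. But the end date already applies most of 4b, so 2.6.3 does not describe what 2.6.2 does, and no reason is given for omitting prophylaxis from the priapic rates.

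What remains is that two end dates are written down and the formula does not restrict its count.

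**Conclusion.** The two definitions in SAP 2.6.2 conflict, and programming the formula as written can give mismatched windows. The possible error by Week 52 is a factor of about 4.0, 2.0 or 1.3 for a subject who changes SCD therapy near Day 91, 183 or 274. For a completer it is an understatement of about 3.4% to 3.7% if no cut-off applies at the final analysis. The first rests on a constant event rate and on combining the prose count with the formula's days; the second rests on how the cut-off is read. The number of subjects affected is unknown.

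The omission of prophylaxis relative to 4b is real, but it is a choice that needs a reason, not a calculation error. The consequence is confined to descriptive secondary rates; the primary test and success rule do not use this formula. The point is worth correcting because the ambiguity is easy to remove.

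**What to change.** In SAP 2.6.2, replace the two definitions with one:

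- Rate = events starting from treatment start up to and including the end date × 365.25 / (end date − start date + 1).
- End date = the earliest of the day before the Week 27 (or Week 53) Day 1 visit, the last treatment-phase contact, last dose + 27 days, the listed SCD-therapy change, and the data cut-off. Keep the 2.1.1 rule for a missed Week 27 or Week 53 visit. Including last contact prevents unobserved days from being counted as event-free.
- For the priapic event rates, add starting or stopping priapism prophylaxis to the list so that it matches 4b, or state why it is left out.

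Then make 2.6.3 agree with the rule actually applied. State how this rate relates to supportive analysis 1 in SAP 2.5.6 and Protocol 12.4.4, which can keep its own self-consistent last-contact definition. List the end-date rule in SAP Section 4 as a change from the protocol.

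The cost is SAP wording and one derivation. No new data are needed.
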